6.25. Adjudication Committees

External adjudication committees will be established to adjudicate cases that meet protocol-defined criteria for liver-related events, and for cardiovascular-related events.

6.25.1. Hepatic Events Adjudication Committee

A key objective of this study is to prevent progression to cirrhosis and associated complications. Clinical events that constitute the clinical outcomes endpoint include:

- 1) Progression to cirrhosis as defined by a liver biopsy showing F4 fibrosis according to the NASH CRN classification, as assessed by the central reader.
- 2) Events of hepatic decompensation including:

- a) Clinically apparent ascites requiring treatment
- b) HE of Grade 2 or above (according to the West Haven criteria defined in [Appendix E](#)) requiring treatment
- c) Portal hypertension-related upper gastrointestinal bleeding identified by endoscopy and requiring hospitalization, including events of bleeding from esophageal varices, gastric varices, and portal hypertensive gastropathy
- 3) Liver transplantation or qualification for liver transplantation, defined as MELD score ≥ 15 (unless due to therapeutic anticoagulation) on at least 2 consecutive occasions at least 4 weeks apart
- 4) All-cause mortality

Each of the clinical events (except histologic progression to cirrhosis, all-cause mortality and liver transplantation) will require confirmation by a Hepatic Events Adjudication Committee. All deaths will be reviewed by this committee to determine if they are liver-related.

If there is clinical evidence that a subject has progressed to cirrhosis (e.g., based on the presence of new esophageal varices, changes in biomarkers [including, but not limited to, low serum albumin, high serum bilirubin, a low platelet count, prolonged INR, or elevated liver stiffness], or development of other clinical signs or symptoms of cirrhosis), the subject should undergo repeat liver biopsy for confirmation of progression to cirrhosis (F4 fibrosis as assessed by the central reader according to the NASH CRN classification) at the discretion of the principal investigator (PI).

Once the clinical event (except histological progression to cirrhosis, all-cause mortality and liver transplantation) is confirmed by the Hepatic Events Adjudication Committee, the subject will discontinue from the study. Subjects who experience histological progression to cirrhosis, all-cause mortality and liver transplantation will be discontinued from the study, but do not require confirmation from the adjudication committee prior to discontinuation.

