7.5. Estimands

In line with ICH E9 (R1) addendum, 5 attributes (treatment, population, endpoint, intercurrent events, and population-level summary) have been specified to translate the primary and key secondary efficacy objectives into treatment effects that are to be estimated (estimands).

The treatment conditions of interest are EFX 28 mg administered weekly, and EFX 50 mg administered weekly, and are compared with matching placebo administered weekly.

The treatment effect is assessed by the primary histological endpoint of improvement in liver fibrosis and no worsening of steatohepatitis.

The population of subjects targeted is adults with NASH with liver fibrosis as defined by the inclusion/exclusion criteria.

Intercurrent events are handled through a composite strategy (see Table 6).

The population-level summary of the treatment effect will be quantified by comparing observed responder proportions supported by the risk ratio of investigational product compared to placebo (EFX 28 mg versus placebo or EFX 50 mg versus placebo) calculated from the odds ratio obtained through Cochran-Mantel-Haenszel (CMH) test detailed in the Statistical Analysis Plan.

Table 6. Approach for Intercurrent Events for the Primary Endpoint

Intercurrent Event	Status
Start of additional therapy with potential to impact NASH condition (i.e. rescue medication)	Subject defined as a non-responder (even if a post-treatment biopsy is available)
MELD score ≥ 15	Subject defined as a non-responder (even if a post-treatment biopsy is available)
Hepatic decompensation event	
Unscheduled biopsy showing progression to F4	Subject will be counted as a non-responder
Bariatric surgery	Subject defined as a non-responder

The estimands attributes for all secondary histological endpoints are defined in the same manner as for the primary endpoint described above.

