3.4 Estimands

In line with ICH E9 (R1) addendum, five attributes (treatment, population, endpoint, intercurrent events, and population-level summary) have been specified to translate the primary efficacy objective into treatment effect that is to be estimated (estimand).

The treatment conditions of interest are EFX 28 mg administered weekly, and EFX 50 mg administered weekly, and are compared with matching placebo administered weekly in addition to standard of care.

CONFIDENTIAL

The population of subjects targeted is adults with NASH with liver fibrosis as defined by the inclusion/exclusion criteria.

The treatment effect is assessed by the primary histological endpoint of improvement in liver fibrosis and no worsening of steatohepatitis at Week 24.

Intercurrent events are handled through a composite strategy (see Table 1).

The population-level summary of the treatment effect will be quantified by comparing observed responder proportions supported by the risk ratio of each investigational product compared to placebo (EFX 28 mg versus placebo or EFX 50 mg versus placebo) calculated from the odds ratio obtained through Cochran-Mantel-Haenszel (CMH) test detailed in the Section 7.6.1.

Table 1 Approach for Intercurrent Events for the Primary Endpoint at Week 24

The estimands attributes for all secondary and exploratory histological endpoints are defined in the same manner as for the primary endpoint described above.

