5.2 Liver Biopsy Analysis Set

The primary analysis set for histological analyses will be the Liver Biopsy Analysis Set (LBAS) which will be a subset of the Full Analysis Set (FAS). It will include all FAS subjects who have baseline and on-study liver biopsy results corresponding to the appropriate time point.

Note: Week 24 and Week 96 LBAS populations may be distinct analysis populations.

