Exploratory: fibrosis stage and NAFLD Activity Score (NAS) on liver histology at Week 24 and Week 96	LBAS PPS
Exploratory: event-free survival (EFS)	FAS
Exploratory: adjudicated cardiovascular endpoints at Week 48, Week 96 and end of study	FAS
Exploratory: bone biomarkers change from baseline	Biomarkers Analysis Set
Exploratory: cardiovascular and metabolic risk factors (e.g., incidence of Type 2 Diabetes, body mass index (BMI), and blood pressure)	Safety Set
Exploratory: non-invasive measures of fibrosis associated with histological regression and/or progression of fibrosis and clinical complications of cirrhosis	LBAS
Exploratory: markers of liver injury and function	FAS LBAS
Exploratory: MRI-PDFF based quantitation of hepatic fat	MRI-PDFF Analysis Set
Exploratory: Plasma concentrations of EFX	PK Analysis Set
Exploratory: waist-to-hip ratio change from baseline	FAS PPS
Exploratory: health-related quality of life (CLDQ-NASH) change from baseline	FAS PPS
Safety Endpoints	
Concomitant medications	Safety Set
Extent of exposure	Safety set
Adverse events (AEs)	Safety set
Laboratory evaluations, electrocardiogram (ECG) and vital sign assessments	Safety set
Bone Mineral Density	Safety Set

CONFIDENTIAL

Statistical Analysis Plan

Sponsor Name: Akero Therapeutics, Inc.
Sponsor Protocol ID: AK-US-001-0102

Outcome Variable	Analysis Set(s)
Endogenous FGF21	Safety Set
Anti-drug antibody (ADA) and neutralizing antibody (NAb)	Safety set

¹ Apply rules for intercurrent events as for primary efficacy endpoint.

6. Data Handling

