7.6.3.2 Liver histology as measured by the fibrosis stage and NAFLD Activity Score

The analysis of fibrosis stage and NAS will be performed using the LBAS and PPS. Fibrosis stage at baseline and post-baseline time points, change from baseline, and shift from baseline frequencies will be summarized by treatment group. In the calculation of change and shift from baseline, fibrosis stage 1A, 1B, and 1C will be considered as stage 1.

In addition, a descriptive summary will present the change from baseline in fibrosis at Week 24 and the change from baseline in fibrosis at week 96, irrespective of change in steatohepatitis.

NAS and components at baseline and post-baseline time points and the change from baseline frequencies together with mean (SD) and median will be summarized by treatment. Shift from baseline frequencies will be presented for the individual components of NAS as well.

7.6.3.3 Proportion of subjects who achieve improvement in liver fibrosis (\geq two stages) and no worsening of steatohepatitis at Week 24 and Week 96

A CMH test will be used to compare the differences in proportions of subjects who achieve improvement in liver fibrosis (\geq two stages) and no worsening of steatohepatitis at Week 24 and Week 96 between the EFX arms and the placebo arm, adjusting for stratification factors. The analysis will be performed using the LBAS. The point estimates and 95% CIs for the differences in proportions, and p-values will be calculated. The 95% CI will be constructed using the Miettinen and Nurminen method. In addition, the same test will be performed to compare the difference in proportions of subjects who achieve two stage improvement in liver fibrosis at Week 24 and Week 96 between the EFX arms and the placebo arm. In addition, the odds ratio and risk ratio point estimate and 95% CI will be summarized for each EFX arm compared to placebo.

The same analysis will be repeated on the PPS for Week 24. The analysis will be repeated using the MFAS, Week 24 LBAS, and Week 96 LBAS at Week 96.

A descriptive summary will present the shift from Week 24 response to Week 96 response for the Week 24 LBAS, subjects with a Week 24 biopsy but missing Week 96 biopsy will be summarized in the missing category in this summary.

CONFIDENTIAL

Statistical Analysis Plan

Sponsor Name: Akero Therapeutics, Inc.
Sponsor Protocol ID: AK-US-001-0102

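### Subjects discontinued after an F4 biopsy read before Day 422 fall out of the Week 96 liver biopsy set and the Week 96 fibrosis stage tables, although the composite strategy treats progression as failure

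*Protocol*

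**What the plan says.** **Discontinuation.** Protocol 6.25.1 defines the histological event as "Progression to cirrhosis as defined by a liver biopsy showing F4 fibrosis according to the NASH CRN classification, as assessed by the central reader". It does not limit this to unscheduled biopsies. The consequence is: "Subjects who experience histological progression to cirrhosis, all-cause mortality and liver transplantation will be discontinued from the study".

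**Intercurrent events.** Protocol 7.5 uses a composite strategy. The F4 row of Table 6 reads "Unscheduled biopsy showing progression to F4" and makes the subject a non-responder. The rules carry over: "The estimands attributes for all secondary histological endpoints are defined in the same manner as for the primary endpoint described above". SAP 3.4 repeats the composite strategy under "Table 1 Approach for Intercurrent Events for the Primary Endpoint at Week 24", but the body of that table is not readable in the public copy. A footnote to SAP Table 3 says of the secondary histology endpoints: "Apply rules for intercurrent events as for primary efficacy endpoint".

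**Analysis set.** SAP 5.2 says of the LBAS: "It will include all FAS subjects who have baseline and on-study liver biopsy results corresponding to the appropriate time point". It adds that the Week 24 and Week 96 versions may differ. SAP 7.6.2 and 7.6.3 analyse the Week 96 responder endpoints first on the LBAS, and SAP Table 4 runs their subgroups on the LBAS.

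**Stage and shift summaries.** SAP 7.6.3.2: "The analysis of fibrosis stage and NAS will be performed using the LBAS and PPS". No FAS version is planned. SAP 7.1 confines a missing category to demographic and baseline tables.

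**The concern.** The trial's own rule takes a known bad outcome out of the set that leads the Week 96 histology analysis. This is not chance dropout, because the reason for absence is the outcome itself. A composite strategy exists so that such subjects count as failures. An analysis set that demands a Week 96 biopsy removes them before that strategy can act.

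Two outputs are affected. The Week 96 LBAS response rate in an arm rises for every progressor removed, which shifts the EFX-placebo difference. The Week 96 stage and shift tables show less progression than occurred, in a protocol that names prevention of progression to cirrhosis as a key objective.

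**Working it through.** The plan states no figure to reproduce: the assumed rates, power and dropout are redacted, and no F4 rate appears. The check is a trace of the rules, followed by an illustration.

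**Timing**
- The Week 24 biopsy may be taken from 2 weeks before to 4 weeks after the visit (Protocol Appendix A). Around Day 169 that is Day 169 - 14 = 155 to Day 169 + 28 = 197.
- SAP 6.1 maps histology on Days 113-421 to Week 24, and from Day 422 to Week 96.
- In long-term follow-up, apart from outcome adjudication, an early termination biopsy is taken only if the last one was at least 12 months earlier (Protocol Appendix B). After a Week 24 biopsy that means Day 155 + 365 = 520 to Day 197 + 365 = 562 at the earliest. Removal soon after Week 24 brings no such biopsy.

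**Where a subject with F4 at the scheduled Week 24 biopsy appears, if removed before a further biopsy**

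| Analysis | Treatment |
|---|---|
| Week 24 LBAS responder analysis | in, non-responder |
| Week 24 stage shift | in, as F4 |
| Week 96 LBAS responder analyses and subgroups | out |
| Week 96 stage and shift (7.6.3.2) | no entry |
| Week 96 repeats on FAS (secondary endpoints) and MFAS | in, non-responder |
| Week 96 repeat on Week 24 LBAS, 7.6.2.1 and 7.6.2.2 | in, non-responder |
| Week 96 repeat on Week 24 LBAS, 7.6.2.3 | in, no missing-data rule stated |
| Week 24 to Week 96 response shift | in, as missing |
| Event-free survival (7.6.3.4) | in, as event |

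The Per Protocol Set is defined on Week 24, so it may retain such a subject, but there is no Week 96 stage to enter and no missing category.

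**Unscheduled F4 before Day 422.** This also maps to the Week 24 window, where SAP 6.1 prefers the scheduled measurement. If a scheduled Week 24 biopsy exists, the F4 read appears in neither the Week 24 nor the Week 96 stage table. Table 6 calls the subject a non-responder, but the subject is not in the Week 96 LBAS to be counted.

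**Size.** From the documents: n = 40 per arm (Protocol synopsis and 5.2.2). Assumed: Week 96 responders rP = 8 on placebo and rE = 20 on EFX; fP and fE subjects removed for F4, each 0 to 4; no other missing biopsies.

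- F4 counted as non-response: rE/n - rP/n = 20/40 - 8/40 = 50.0% - 20.0% = 30.0 points.
- F4 dropped: rE/(n - fE) - rP/(n - fP).

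| fP / fE | Placebo | EFX | Difference | Change |
|---|---|---|---|---|
| 2 / 0 | 8/38 = 21.1% | 20/40 = 50.0% | 28.9 | -1.1 |
| 4 / 0 | 8/36 = 22.2% | 50.0% | 27.8 | -2.2 |
| 2 / 1 | 21.1% | 20/39 = 51.3% | 30.2 | +0.2 |
| 4 / 4 | 22.2% | 20/36 = 55.6% | 33.3 | +3.3 |
| 0 / 4 | 8/40 = 20.0% | 55.6% | 35.6 | +5.6 |

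With 10 and 24 responders instead, the extremes are -2.8 (4/0) and +6.7 (0/4).

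Removal multiplies an arm's rate by n/(n - f), so one F4 subject moves the higher-responding arm more. At these assumed rates, placebo needs roughly 50/20 = 2.5 times as many F4 subjects as EFX before the net effect understates EFX. This is why 2/1 is slightly positive.

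In the Week 96 stage table, each omitted F4 subject is 1/40 = 2.5 points of the arm, or 10 points for four.

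**The case against.** The strongest reply is that the plan already covers these subjects almost everywhere else. The Week 96 secondary responder endpoints are repeated on the FAS, the MFAS and the Week 24 LBAS. The Week 24 LBAS repeat, with missing as non-response, is in substance the analysis asked for. Event-free survival on the FAS counts central F4 reads as events, so cumulative progression is reported. The stage table is exploratory and descriptive. All of this stands, and it limits the point. It does not change the lead Week 96 set or its subgroups, and no repeat covers the stage and shift tables.

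Four stronger readings are tempting, and the documents do not support them:

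- *That the word restricting Table 6 to unscheduled biopsies is the cause.* Exclusion comes from discontinuation plus LBAS membership. Changing Table 6 alone would return nobody to the Week 96 LBAS. At Week 24 itself, F4 in a subject who entered at F2 or F3 is non-response by definition.
- *That progressors vanish from the trial's histology.* The trace shows where they remain.
- *That the Week 96 table can show only F4 first found at the Week 96 biopsy.* An unscheduled or early termination F4 biopsy from Day 422, within 21 days of the last dose, maps to Week 96. The documents also do not say when a blinded, unpaired read reaches the site. Removal after about Day 520-562 could bring an early termination biopsy in the Week 96 window.
- *That a stated share of progression is lost, or that the bias favours EFX.* With no F4 rate given, any share rests on assumption, and the sign can go either way.

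It is also fair to object that entering a Week 24 F4 as the Week 96 stage would report a stage not observed then. The fix avoids that.

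**Conclusion.** The point holds in a limited form. A subject discontinued for F4 before Day 422, with no later biopsy, is missing from the lead Week 96 LBAS responder analyses, from their LBAS subgroups and from the Week 96 stage and shift tables. That is outcome-dependent exclusion, at odds with the stated composite strategy.

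F4 removals on placebo alone understate the EFX benefit, and removals on EFX alone overstate it. With both, the net effect depends on the counts and on the response rates. The illustrated movement of about -2 to +6 points rests on 40 per arm, 8 and 20 responders, at most 4 F4 subjects per arm and no other missing biopsies. It is not an estimate of what will happen.

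The restriction to unscheduled biopsies is confirmed for Protocol Table 6 only, since the body of SAP Table 1 cannot be read. This is a cheap improvement, not a threat to the primary Week 24 analysis.

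**What to change.** - **SAP 5.2, 7.6.2 and 7.6.3:** keep any subject with a centrally read F4 biopsy at or before Week 96 in the Week 96 LBAS, as a non-responder.
- **SAP 7.6.3.2:** show these subjects in the Week 96 shift table in a separate row, *F4 on earlier biopsy, discontinued*, with the count footnoted, and not as an observed Week 96 stage.
- **Protocol Table 6, and SAP Table 1 if it reads the same:** make the F4 row cover any centrally read biopsy up to the endpoint's time point, and reconcile it with Protocol 6.25.1. This supports the two SAP changes but does not replace them.

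No view is taken on the discontinuation rule itself.

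The cost is SAP and table-shell wording. It needs no new data, because the F4 reads are already collected. The downside is that a few Week 96 entries rest on an earlier biopsy and must be footnoted.

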6.25.2. Cardiovascular Events Adjudication Committee

Cardiovascular events including cardiovascular death, myocardial infarction, stroke, hospitalization for unstable angina, hospitalization for cardiac failure, and urgent or emergency visits for urgent heart failure will be adjudicated by an independent Cardiovascular Events Adjudication Committee. All deaths will be reviewed by this committee to determine if they are cardiovascular-related. Subjects experiencing a cardiovascular event will be allowed to continue in the study at the discretion of the PI.

6.26. Observation for Drug Induced Liver Injury (DILI)

Throughout the study, all TEAEs, clinical assessments, and clinical laboratory parameters, and the criteria for potential drug-induced liver injury will be closely monitored with subjects entering close observation as detailed in this protocol.

6.26.1. Subjects with Normal Liver Transaminases and Bilirubin at Baseline

Drug-induced liver injury monitoring in subjects with normal liver transaminases and bilirubin at baseline should be performed throughout the study according to the procedures summarized below.

- If subjects with normal baseline liver indices develop elevations in ALT of $>5 \times$ ULN during the study, repeat testing should be performed within 2 - 5 days from receipt of results.
 - If there are persistent elevations (ALT $>5 \times$ ULN or TBL $>2 \times$ ULN) upon repeat testing, close observation (testing and physical examination 2 to 3 times per week) should be implemented. An important purpose of the close observation is to gather additional clinical information to seek other possible causes of the observed liver test abnormalities, such as one of the following: acute viral hepatitis, alcoholic and autoimmune hepatitis, hepatobiliary disorders, cardiovascular causes, or concomitant treatments. Discontinuation of investigational medicinal product should be considered.
- Study drug should be discontinued, and the subject should be followed until resolution of signs or symptoms, in the following situations:
 - ALT $>8 \times$ ULN
 - ALT $>5 \times$ ULN and (TBL $>2 \times$ ULN)
 - ALT $>5 \times$ ULN with the appearance of fatigue, nausea, vomiting, right upper quadrant pain or tenderness, fever, rash, and/or eosinophilia ($>5\%$) as assessed by the PI to indicate hepatic injury

For any subjects who present with a constellation of syndromes indicative of liver disease as per the Investigator's overall assessment (i.e., fatigue, nausea, vomiting, right upper quadrant pain or tenderness, fever, rash, and/or eosinophilia [$> 5\%$]), perform liver function tests to determine if liver disease is worsening.

Re-initiation of investigational medicinal product may be considered after consultation with the Medical Monitor and DMC assessment.

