6.23. Adverse Events of Special Interest

The Investigator will monitor each subject for clinical and laboratory-evidence for predefined AEs of special interest (AESIs) throughout the subject's participation in this study. The Investigator should treat the AESI according to local standard of care. The following conditions will be monitored as AESIs during this study:

- Injection Site Reactions

- Diarrhea
- Hypoglycemia
- Neurological and Psychiatric Events
- Drug-induced liver injury

Drug-induced liver injury will be monitored and managed according to [Section 6.26](#).

During the course of the study, additional AESIs may be identified by the Sponsor. The Investigator will assess and record in detail any additional information for AESIs on the AE eCRF form.

Subjects who experience gastrointestinal adverse events while on study should be managed according to local standard of care including concomitant medications to manage symptoms.

6.24. Clinical Laboratory Abnormalities and Other Abnormal Assessments as Adverse Events or Serious Events

Laboratory abnormalities are usually not recorded as AEs or SAEs, however, laboratory abnormalities (e.g., clinical chemistry, hematology, urinalysis) independent of the underlying medical condition that require medical or surgical intervention or lead to investigational medicinal product interruption or discontinuation must be recorded as an AE, as well as an SAE, if applicable. In addition, laboratory or other abnormal assessments (e.g., electrocardiogram, X-rays, vital signs) that are associated with signs and/or symptoms must be recorded as an AE or SAE if they meet the definition of an AE (or SAE) as described in [Section 6.22](#). If the laboratory abnormality is part of a syndrome, record the syndrome or diagnosis (e.g., anemia) not the laboratory result (i.e., decreased hemoglobin). Severity should be recorded and graded according to the CTCAE Version 5.0. For AEs associated with laboratory abnormalities, the event should be graded based on the clinical severity in the context of the underlying conditions; this may or may not be in agreement with the grading of the laboratory abnormality.

Toxicity Management

Any questions regarding toxicity management should be directed to the Medical Monitor.

Grade 1 and 2 Laboratory Abnormality or Clinical Event

Continue investigational medicinal product at the discretion of the Investigator.

Grade 3 Laboratory Abnormality or Clinical Event

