6.26.2. Subjects with Elevations in Liver Transaminases or Bilirubin at Baseline

Drug-induced liver injury monitoring in subjects with elevations in liver transaminases or bilirubin at baseline should be performed throughout the study according to the procedures summarized below.

- If subjects with abnormal baseline liver indices develop elevations of ALT $>3 \times$ baseline or ≥ 300 U/L (whichever occurs first) during the study, repeat testing should be performed within 2 - 5 days.

- If there are persistent elevations (ALT $>3 \times$ baseline, or ≥ 300 U/L) upon repeat testing, then close observation (testing and physical examination 2 to 3 times per week) should be implemented and discontinuation of study drug should be considered.
- Discontinue the study drug if any of the following occur:
 - ALT increases to $>5 \times$ baseline measurements or ≥ 400 U/L (whichever occurs first).
 - ALT increase $>3 \times$ baseline measurements or ≥ 300 U/L (whichever occurs first) AND the increase is accompanied by a concomitant increase in TBL to $> 2 \times$ ULN.
 - ALT increase $>3 \times$ baseline measurements or ≥ 300 U/L (whichever occurs first) with the appearance of fatigue, nausea, vomiting, right upper quadrant pain or tenderness, fever, rash, and/or eosinophilia ($> 5\%$)

For any subjects who present with a constellation of syndromes indicative of liver disease as per the Investigator's overall assessment (i.e., fatigue, nausea, vomiting, right upper quadrant pain or tenderness, fever, rash, and/or eosinophilia [$> 5\%$]), perform liver function tests to determine if liver disease is worsening.

Re-initiation of investigational medicinal product may be considered after consultation with the CRO Medical Monitor and DMC assessment.

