7.13. Data Monitoring Committee

An external DMC that consists of two hepatologists, one cardiologist and a statistician will review the progress of the study. The DMC will convene after 45 subjects (approximately 15 per treatment group) have completed the Week 12 assessments. The DMC will receive all reports of SAEs, potential DILI events for evaluation and convene as needed to monitor for safety and additional meetings will be scheduled as required. The DMC will provide recommendations to Akero whether the nature, frequency, and severity of adverse effects associated with study treatment warrant the early termination of the study in the best interests of the participants, whether the study should continue as planned, or the study should continue with modifications. The DMC may also provide recommendations as needed regarding study design.

The DMC will monitor study progress, tracking the actual annual event rate for the outcomes endpoint compared with the assumed prevalence rate per year.

Due to the challenge of recognizing and diagnosing DILI in subjects with pre-existing hepatic dysfunction, the DMC will review potential cases of DILI (refer to [Section 6.26](#)). Subjects will be categorized as those for whom DILI or worsening of hepatic function attributable to study drug could be excluded (e.g., a clear, alternative explanation exists); those for whom DILI or worsening of hepatic function attributable to study drug could not be excluded (e.g., no clear, alternative explanation exists); and those with insufficient data to make a determination. Subjects experiencing DILI will be allowed to continue in the study according to the follow-up procedures outlined in Section 6.26.

The DMC's specific activities will be defined by a mutually agreed charter, which will define the DMC's membership, conduct, and meeting schedule.

While the DMC will be asked to advise Akero regarding future conduct of the study, including possible early study termination, Akero retains final decision-making authority on all aspects of the study.

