ALT	Alanine aminotransferase increased	>ULN - 3.0 x ULN if baseline was normal; 1.5 - 3.0 x baseline if baseline was abnormal	>3.0 - 5.0 x ULN if baseline was normal; >3.0 - 5.0 x baseline if baseline was abnormal	>5.0 - 20.0 x ULN if baseline was normal; >5.0 - 20.0 x baseline if baseline was abnormal	>20.0 x ULN if baseline was normal; >20.0 x baseline if baseline was abnormal
AST	Aspartate aminotransferase increased	>ULN - 3.0 x ULN if baseline was normal; 1.5 - 3.0 x baseline if baseline was abnormal	>3.0 - 5.0 x ULN if baseline was normal; >3.0 - 5.0 x baseline if baseline was abnormal	>5.0 - 20.0 x ULN if baseline was normal; >5.0 - 20.0 x baseline if baseline was abnormal	>20.0 x ULN if baseline was normal; >20.0 x baseline if baseline was abnormal
TBILI	Blood bilirubin increased	>ULN - 1.5 x ULN if baseline was normal; >1.0 - 1.5 x baseline if baseline was abnormal	>1.5 - 3.0 x ULN if baseline was normal; >1.5 - 3.0 x baseline if baseline was abnormal	>3.0 - 10.0 x ULN if baseline was normal; >3.0 - 10.0 x baseline if baseline was abnormal	>10.0 x ULN if baseline was normal; >10.0 x baseline if baseline was abnormal
ALP	Alkaline phosphatase increased	>ULN - 2.5 x ULN if baseline was normal; 2.0 - 2.5 x baseline if baseline was Abnormal	>2.5 - 5.0 x ULN if baseline was normal; >2.5 - 5.0 x baseline if baseline was Abnormal	>5.0 - 20.0 x ULN if baseline was normal; >5.0 - 20.0 x baseline if baseline was abnormal	>20.0 x ULN if baseline was normal; >20.0 x baseline if baseline was abnormal

CONFIDENTIAL

Statistical Analysis Plan

Sponsor Name: Akero Therapeutics, Inc.
 Sponsor Protocol ID: AK-US-001-0102

Serum Chemistry	CTCAE Term	Grade 1	Grade 2	Grade 3	Grade 4
Creatinine (Cr)	Creatinine increased	>ULN - 1.5 x ULN	>1.5 - 3.0 x baseline; >1.5 - 3.0 x ULN	>3.0 x baseline; >3.0 - 6.0 x ULN	>6.0 x ULN
CPK	CPK increased	>ULN - 2.5 x ULN	>2.5 - 5.0 x ULN	>5 - 10 x ULN	>10 x ULN
Potassium (K)	Hyperkalemia	>ULN - 5.5 mmol/L	>5.5 - 6.0 mmol/L	>6.0 - 7.0 mmol/L	>7.0 mmol/L
Amylase	Serum amylase increased	>ULN - 1.5 x ULN	>1.5 - 2.0 x ULN; >2.0 - 5.0 x ULN and NCS	>2.0 - 5.0 x ULN and CS; >5.0 x ULN and NCS	>5.0 x ULN and CS
Glucose	Hypoglycemia	<LLN - 55 mg/dL; <LLN - 3.0 mmol/L	<55 - 40 mg/dL; <3.0 - 2.2 mmol/L	<40 - 30 mg/dL; <2.2 - 1.7 mmol/L	<30 mg/dL; <1.7 mmol/L

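### Section 6.26.1 lets bilirubin count only after ALT has passed 5 x ULN, so a TBL above 2 to 3 x ULN with lower ALT has no mandatory numeric trigger, while 6.26.2 can require a stop at almost the same values

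*Protocol*

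**What the plan says.** **Protocol 6.26.1 (normal transaminases and bilirubin at baseline).** The sequence opens with "If subjects with normal baseline liver indices develop elevations in ALT of" more than 5 x ULN, in which case "repeat testing should be performed within 2 - 5 days from receipt of results". If ALT above 5 x ULN or TBL above 2 x ULN persists "upon repeat testing, close observation (testing and physical examination 2 to 3 times per week) should be implemented". Then: "Study drug should be discontinued, and the subject should be followed until resolution of signs or symptoms, in the following situations". Three situations follow: ALT above 8 x ULN; ALT above 5 x ULN with TBL above 2 x ULN; ALT above 5 x ULN with symptoms. A closing paragraph asks for liver tests in subjects whose symptoms suggest liver disease.

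**Protocol 6.26.2 (transaminases or bilirubin raised at baseline).** One of its stop rules is ALT above 3 x baseline, or 300 U/L and over, "AND the increase is accompanied by a concomitant increase in TBL to" more than 2 x ULN.

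**Protocol 6.24 (toxicity management).** For Grade 1 and 2: "Continue investigational medicinal product at the discretion of the Investigator". A Grade 3 laboratory abnormality that is clinically significant, confirmed on repeat and considered related leads to withholding. A confirmed, clinically significant Grade 4 abnormality leads to a DMC causality assessment. Section 6.20 lists Grade IV events and the 6.26 criteria as mandatory discontinuations.

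**SAP 7.7.3, Table 6.** Grade 2 bilirubin is ">1.5 - 3.0 x ULN if baseline was normal". Grade 2 ALT, with normal baseline, is above 3.0 and up to 5.0 x ULN.

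**Protocol 7.13.** Here "the DMC will review potential cases of DILI", with the cases identified by pointing back to 6.26.

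**The concern.** A combined rise in ALT and bilirubin is a pattern that 6.26 is written to catch. In 6.26.1 the bilirubin criterion sits behind an ALT-only gate. A subject with normal baseline tests can therefore have TBL above 2 x ULN and a several-fold ALT rise without meeting any numeric step of the section. Sections 6.20 and 7.13 both rely on 6.26, so the omission carries into mandatory discontinuation and DMC referral.

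A subject whose baseline ALT lay just over the ULN would, with the same on-study values, fall under 6.26.2 and have to stop. The protocol gives no reason for the change.

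Timing adds to this. The schedules of assessments place chemistry every 4 weeks from Week 4 to Week 56 and every 8 weeks after that, while dosing is weekly. Without a mandated retest, the next scheduled sample can be 4 or 8 weeks away.

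**Working it through.** The plan has no figure to reproduce here. The check applies the written rules to combinations of ALT and TBL.

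**Inputs.** The thresholds come from Protocol 6.26.1, 6.26.2, 6.24 and 6.20, and the grade limits from SAP Table 6. Table 6 is an analysis table, but it is based on CTCAE v5.0, which Protocol 6.22.1 and 6.24 also use. The documents do not give the ALT ULN, so it is assumed at 30, 40, 55 and 70 U/L. Normal is taken as at or below ULN.

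**Step 1: 6.26.1 alone.** The retest needs ALT above 5 x ULN, and each stop rule needs at least that. The rules were run for ALT from 1.0 to 5.0 x ULN and TBL from 2.1 to 10.1 x ULN. The result was no retest and no stop at every point. At ALT 5.1 x ULN with TBL 2.1 x ULN, both appear.

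**Step 2: add the general toxicity rules** (normal baseline, ALT up to 5 x ULN, so ALT is at most Grade 2).

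| TBL | Grade | What the protocol mandates |
|---|---|---|
| above 2 to 3 x ULN | 2 | Nothing numeric; dosing left to the Investigator (6.24) |
| above 3 to 10 x ULN | 3 | Withhold if clinically significant, confirmed and related (6.24) |
| above 10 x ULN | 4 | DMC causality assessment (6.24) and discontinuation (6.20) |

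The protocol-wide gap is therefore the first row only.

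**Step 3: compare with 6.26.2.** With TBL above 2 x ULN and baseline ALT equal to b x ULN, 6.26.2 requires a stop when ALT exceeds 3b x ULN or reaches 300 U/L. Section 6.26.1 is silent up to 5 x ULN. The two differ from 3b x ULN to 5 x ULN:

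- b = 1.02: 3 x 1.02 = 3.06, so from just above 3.06 to 5 x ULN.
- b = 1.2: from just above 3.6 to 5 x ULN.
- b = 1.5: from just above 4.5 to 5 x ULN.
- b of 5/3 = 1.67 or more: no difference while ULN is below 60 U/L. At higher ULN the 300 U/L limit takes over; at ULN 70, 300/70 = 4.29 x ULN.

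A subject placed in 6.26.2 by raised bilirubin, with baseline ALT 0.75 x ULN, must stop above 3 x 0.75 = 2.25 x ULN.

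**Step 4: example.** Take ULN 40 U/L, AST and bilirubin normal at baseline, on-study ALT 130 U/L and TBL 2.5 x ULN.

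- Baseline ALT 39: 6.26.1 applies. 130/40 = 3.25 x ULN, which is below 5, so no action is specified.
- Baseline ALT 41: 6.26.2 applies. 130/41 = 3.17 x baseline, which is above 3, so a stop is mandatory.

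These U/L values are tied to ULN 40. At ULN 30 both baselines are abnormal and both subjects stop (130/39 = 3.33; 130/41 = 3.17). At ULN 55 both are normal and neither stops (130/55 = 2.36 x ULN). The contrast carries over only if all ALT values are rescaled with the ULN.

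**The case against.** The strongest reply is that 6.26 does not stand alone.

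- Section 6.23 requires the Investigator to watch clinical and laboratory evidence for drug-induced liver injury (DILI).
- SAP 3.5 sends suspected DILI to the DMC without a numeric threshold, and close observation under 6.26.3 applies to any suspected case.
- Section 6.22 requires clinically significant laboratory abnormalities to be followed, and 6.20 allows a stop on judgment.
- SAP 7.7.3 plots each subject's peak ALT against total bilirubin (eDISH), and AST against bilirubin, whether or not 6.26 is met.

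All of this stands. A reader might infer that such cases are barred from DMC review, or that liver injury will be under-reported. The documents do not support either inference: these routes depend on judgment or come at analysis, but they exist.

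Two further replies stand in part. The bilirubin limb of 6.26.1 is not dead, because after a first ALT above 5 x ULN the repeat may show ALT falling and TBL above 2 x ULN. That still leaves bilirubin unable to start the sequence. Also, the two sections cover mutually exclusive groups, so they do not give one patient opposite orders. This is a step at the baseline cut, from no instruction to a stop, and nothing explains it.

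A reader might also infer that any bilirubin rise in a normal-baseline subject goes unaddressed, or that 6.26.2 would stop every such subject. Step 2 rules out the first above TBL 3 x ULN, subject to the Grade 3 conditions. On the second, 6.26.2 also enters through ALT and requires no stop at or below 3 x baseline with ALT under 300 U/L.

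**Conclusion.** The inconsistency is real and can be read directly from the text. Within 6.26.1 the entry trigger does not match the section's own bilirubin criterion. Across the protocol, normal-baseline subjects with TBL above 2 and up to 3 x ULN and ALT up to 5 x ULN have no mandatory numeric trigger for a retest, close observation, a stop or DMC referral. When baseline ALT is just above the ULN, 6.26.2 differs over ALT of about 3 to 5 x ULN; the band narrows as baseline ALT rises.

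The gap itself is stated in multiples of ULN and does not depend on the assumed ULN; only the worked example and the 300 U/L limit do. The documents do not say how many subjects have normal baseline tests, so the number affected cannot be estimated. The defect is the missing mandatory trigger. It bears on subject safety and is cheap to resolve.

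**What to change.** - Reconcile the entry trigger of 6.26.1 with the bilirubin limb in its next step, and make clear what has to persist on the repeat test.
- Reconcile the combined ALT and bilirubin criterion of 6.26.1 with that of 6.26.2, or state the reason for the difference.
- State whether AST counts. The section headings speak of transaminases, but the numeric criteria in 6.26.1 and 6.26.2 use only ALT and TBL.
- Align 6.20, 6.24 and 7.13 with the result, so that discontinuation, toxicity management and DMC referral rest on the same definition.

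The sponsor's clinical team decides the values and actions; none is proposed here. The cost is protocol wording, a laboratory alert update and a few extra repeat draws.
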